3.3. Result and primary Outcome

Primary Outcome

✓ SARS-CoV-2 infection defined as:

- Detection of SARS-CoV-2 nucleic acid using RT-PCR in any of the specimens collected during the study-follow-up including the asymptomatic participant

-Positive IgG antibodies against SARS-CoV-2 in any of the specimens collected during the study-follow-up

Secondary outcomes

- Serious and non-serious adverse events

- Discontinuation of using the intervention (TDF/FTC or placebo) for any reason

- Adherence to TDF/FTC defined as: number of tablets taken/total number of dispensed tablets

- Severity of SARS-CoV-2 infections according to the following categories:

[figure not shown]
- Asymptomatic infection.

- Mild symptomatic SARS-CoV-2 infection with no need for hospitalization.

- Moderate symptomatic SARS-CoV-2 infection that requires hospitalization, but no ICU.

- Severe SARS-CoV-2 infection: dyspnea with other SARS-CoV-2 symptoms requiring ICU hospitalization.

Graph 1. Flowchart of assignments and follow up of the clinical trial.

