3.4. Sample size

An estimative of the number of required participants was done according to the following parameters:

- Risk of SARS-CoV-2 infection reported in the world: despite of the little data available on incidence reports from China, The Netherlands and Madrid vary from 6 to 38.9 per 100 exposed health care workers. The high variability on the incidence is related to the develop of institutional outbreaks, thus establishing a latent risk in all hospital institutions in a pandemic scenario (7,44,76). To assess the sampling size calculation for this study, besides what has been reported internationally, an approximate calculation of the incidence of SARS-CoV-2 infection in the health care institutions in which the study will be held was performed. It is important to know the infection and epidemic control variates from one institution to another. While some actively screen asymptomatic health care personnel others only screen symptomatic health care personnel. The incidence observed in a 2-month period of time variates between 3.3% and 13.7% with a mean of 11.2 cases per 100 health care workers.

Based on that preliminary information, an expected risk for SARS-CoV-2 infection in the control group (Placebo + PPE) of 0.10 was used for the calculation. With the objective of estimating precisely a 50% relative risk reduction an assumption of an expected risk of 0.05 was done in the intervention group (Tenofovir/Emtricitabine + PPE) in order for a difference of 0.05 to detect between both groups.

- Power: 0,80. Alfa level: 0.05
- Assigantion ratio $n_1/n_2 = 1:1$ (randomization1: 1).
- Sample size: 858 (429 per group).

Considering possible loses up to 10% it is risen to 950 in total (with randomization 475 participants to each group).

As a limitation of the study, if the incidence or the effect of the interventions are considerably lower than expected, the power to detect significant differences between both groups will be reduce. However, due to the progression of the pandemic in our country, with a tendency to increase, it is probable that the incidence observed in health care professionals will remain stable or even increase not only for the intrahospital risk, but for the risk in the community,

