3.6.3. Randomization

A simple randomization will be carried out, considering that it is not deemed necessary to stratify by any characteristics of the individuals, or by center. Additionally, due to the size of the sample there is little possibility of presenting a significant imbalance between the groups regarding characteristics that affect the outcome.

The randomization will be carried out with a 1:1 relationship between the active intervention and the placebo, a randomization system generated by the REDCap software will be used, with random numbers that will meet the following requirements: each volunteer will have a known probability, and equal to be assigned to any of the interventions, future assignments will not be predictable based on previous assignments, the order of assignment will be reproducible.

The randomization will be carried out centrally, by a trained member of the HUSI research office, who is not part of the research group, or the study staff, after generating the randomization, this will be communicated exclusively to the central pharmacist of the research team.

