The hazard ratio will be estimated by comparing the risk of infection in the intervention group (TDF/FTC + EPP), with the risk in the control group (placebo + EPP), with a confidence interval of 95 %, using a univariate Cox regression model.

If necessary, adjustment will be made for variables that may affect the occurrence of the primary outcome and that are not balanced between the intervention group and the placebo group; The need for adjustment with an OR greater than 1.5 will be considered for dichotomous categorical

variables, such as sex; or if there are differences between the groups greater than 0.25 of the standard deviation for continuous variables such as age, adherence to pharmacological intervention or EPP, and hours of exposure to the COVID area. For the calculation of the adjusted hazard ratio, a multivariate Cox proportional hazards model will be used, if the proportionality assumption is met, or an extended Cox model if this assumption is not met.

For secondary outcomes

-The proportion of incidence of total adverse effects in each group will be determined at day 60 after randomization, estimated as the cumulative incidence using the Kaplan Meier method.

The hazard ratio ("Hazard Ratio") will be estimated by comparing the risk of adverse events in the intervention group (TDF/FTC + EPP), with the risk in the control group (placebo + EPP), with a confidence interval of 95%, using a univariate Cox regression model.

Additionally, the same analysis will be performed for serious adverse events.

- The proportion of incidence of discontinuation of the intervention in each group, for any reason, will be determined at day 60 after randomization, estimated as the cumulative incidence using the Kaplan Meier method.

The hazard ratio will be estimated by comparing the discontinuation of the intervention in the intervention group (TDF/FTC + EPP), with the risk in the control group (placebo + EPP), with a confidence interval of 95 %, using a univariate Cox regression model.

- It will be determined as the difference in the mean or median (according to the distribution of the data) of the percentage in which the individuals were adherent

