6.1. Definitions

- Adverse event (AE)

Any adverse medical occurrence in a patient or subject of a clinical investigation to whom a pharmaceutical product was administered and that does not necessarily have a causal relationship with this treatment. Therefore, an adverse event (AE) can be any unfavorable and unintended sign (including an abnormal laboratory finding), symptom or illness temporarily associated with the use of a medicinal (research) product, whether it is related. (104).

Considering the above, the United States National Institute of Health in conjunction with the National Cancer Institute of the same country published standardized definitions of adverse events known as Common Terminology Criteria for Adverse Events (CTCAE). Events, for its acronym in English), to describe the severity of the organic damage caused to patients by the various medications (104,105). According to them, the following events are considered:

- Serious adverse event (SAE)

Any unfavorable occurrence than at any dose that:

- Results in death.
- Is life threatening, requires hospitalization of the patient or prolongation of existing hospitalization.
- Results in persistent or significant disability / disability.
- Generates a congenital anomaly / birth defect.

- Fatal Serious Adverse Event.

EAS that end in the death of the subject or threaten the life of the same.

- Expected / Listed Serious Adverse Event.

EAS whose specificity or severity is consistent with that described in the Research Protocol, Investigator's Manual / basic prescription information or product label.

- Unexpected / Unlisted Serious Adverse Event.

EAS whose specificity or severity is not consistent with that described in the Research Protocol, Investigator's Manual / basic prescription information or product label.

- Non-Serious adverse event

All other events that do not meet any of the EAS seriousness criteria

- Adverse event requested

They are the AE that will be searched for in each assessment of the subjects participating in the study.

- Unsolicited adverse events

They are the AEs that are voluntarily manifested by the patient that may or may not be related to the study drug.

6.2. Assessment and documentation of adverse events.

The researcher assigned to follow up the study subjects will be responsible for recording all adverse events in each participating institution, regardless of the group evaluated, with the following exceptions:

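### The safety analyses do not separate COVID-19 events from other adverse events, so if the drug works the AE and SAE hazard ratios mix efficacy with harm

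*Combined protocol and SAP*

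**What the plan says.** - **Section 4, secondary outcomes.** The cumulative incidence of total adverse events is estimated at day 60 by Kaplan-Meier, with a hazard ratio from a univariate Cox model. For SAEs: "Additionally, the same analysis will be performed for serious adverse events". No rule removes COVID-19 events, and no second analysis without them is planned. Infection ends follow-up only in the text on the primary outcome.
- **Section 6.1.** An adverse event is "Any adverse medical occurrence in a patient or subject of a clinical investigation to whom a pharmaceutical product was administered", with no causal link required. The definition goes on to cover any symptom or illness. Hospitalisation is one of the SAE criteria.
- **Section 3.3.** COVID-19 admissions also define an outcome on the efficacy side. One severity category is "Moderate symptomatic SARS-CoV-2 infection that requires hospitalization, but no ICU", and the next is ICU care.
- **Section 6.2.** All adverse events are recorded subject to exceptions, but no list of exceptions appears in the available text.
- **Appendix 3.** The AE variable is limited to events during product administration. The SAE variable joins threat to life and hospitalisation with *and*, unlike section 6.1.
- **Section 3.6.9 (procedure when the primary outcome occurs).** At a positive RT-PCR or IgG the product is suspended and masking is released.

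**The concern.** Safety shares the general objective with effectiveness. Section 4.1 explains that there will be no data monitoring committee, so these end-of-trial comparisons carry much of the safety conclusion.

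A hazard ratio for all AEs or all SAEs has two parts: events the drug may cause, and infections the drug is meant to prevent. If it prevents infections, the second part pulls the ratio below the value for the first. A real excess of other serious events could then look neutral, or a neutral profile could look protective. This happens when the drug works, which is when a reassuring safety ratio would most influence wider use.

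Some recorded terms overlap as well. Headache is both a COVID-19 symptom code and an AE code in Appendix 3. Fatigue is a testing trigger in section 3.6 and an AE code in Appendix 3.

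**Working it through.** **Inputs from the plan (section 3.4).** Control risk: "an expected risk for SARS-CoV-2 infection in the control group (Placebo + PPE) of 0.10 was used for the calculation". Active risk: "assumption of an expected risk of 0.05 was done in the intervention group". Also "Power: 0,80. Alfa level: 0.05", with 1:1 allocation (section 3.6.3).

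**The plan's own figure.** Two-sided, without continuity correction, 0.10 versus 0.05 needs 435 per arm (870) with pooled variance, or 432 per arm (864) unpooled. The plan's "Sample size: 858 (429 per group") is within 1.4% of these. Allowing for 10% losses, 858/0.90 = 953.3, or 954, against the stated 950. The 10% and 5% are therefore the real design values and are used below.

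**Assumptions (not in the documents).** 3-15% of infections are hospitalised, and non-COVID SAE risk on placebo is 0.5-2%. COVID-19 and other events are taken as independent.

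**Formulas.** Combined risk per arm p = 1 - (1 - a)(1 - b), where a is the non-COVID risk and b is infection risk times hospitalised share. Hazard ratio = ln(1 - p_active) / ln(1 - p_control).

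**Worked case: 10% hospitalised, background 0.5%, non-COVID SAE risk doubled to 1%.**
- Control: 1 - 0.995 x 0.99 = 1.50%
- Active: 1 - 0.99 x 0.995 = 1.50%
- Hazard ratio 1.00, although the non-COVID ratio is 2.01

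**SAE hazard ratio as it would read (no true harm / non-COVID risk doubled):**

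| Hospitalised share | Background 0.5% | 1% | 2% |
|---|---|---|---|
| 3% | 0.81 / 1.44 | 0.88 / 1.66 | 0.94 / 1.82 |
| 10% | 0.67 / 1.00 | 0.75 / 1.25 | 0.83 / 1.52 |
| 15% | 0.62 / 0.87 | 0.70 / 1.10 | 0.79 / 1.37 |

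In the central cell (10%, 1%), approximate power at 475 per arm to detect the doubling falls from 24% (1% v 2%) to 8% (1.99% v 2.49%).

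**No efficacy (10% infected in both arms).** No true harm reads 1.00. A doubling reads between 1.25 (15% hospitalised, 0.5% background) and 1.89 (3%, 2%). This is dilution toward 1, never reversal.

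**Total AEs.** Assume 15% background and symptomatic infection of 8% v 4%.
- Control event-free: 0.85 x 0.92 = 0.782
- Active, true hazard ratio 1.2: 0.85^1.2 x 0.96 = 0.790, which reads 0.96
- Active, true risk ratio 1.2: 0.82 x 0.96 = 0.787, which reads 0.97

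The 8% is near the top of what the plan's background supports: section 1.3 gives 18-46.5% asymptomatic, so 5.35-8.2% symptomatic out of 10%. At the low end (5.35% v 2.675%) the two readings are 1.02 and 1.04. At 40% background with 8% v 4%, a true hazard ratio of 1.2 reads 1.10. The distortion shrinks as AEs become common.

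**The case against.** **Inclusion is not stated.** A reader might infer that the plan definitely counts COVID-19 as an AE and SAE. The documents do not support that. The exceptions in section 6.2 may cover outcome events, and their absence may come from text conversion. Under Appendix 3, an admission after product is suspended could fall outside the AE window, and an admission without threat to life could fall outside the SAE criterion. This stands, and it makes the point conditional. It does not remove it: section 3.6 keeps participants on product while RT-PCR is awaited, so symptom onset falls within the window. A hospitalisation under high suspicion is itself a trigger for suspension, so it can begin on product.

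**The overlap of terms is limited.** A reader might also take diarrhoea and malaise as double-coded. Malaise is not a listed AE term, and diarrhoea is listed only as an SAE type. Headache and fatigue do overlap.

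**Separation is already possible.** The AE form records relation to the drug, the causality grades consider concurrent disease, severity is reported by arm, and the relevant dates are collected. This stands as a reason why the fix is cheap. Relation to the drug is not relation to infection, however, and section 4 analyses total events.

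**The sizes are assumed, and SAE power is low anyway.** This stands too. In the table a doubling still reads above 1 in seven of nine cells, so complete masking is a corner case. At 24% power for 1% v 2%, no firm SAE conclusion was available even without mixing.

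**Exclusion has its own bias.** Attribution to infection after masking is released could differ by arm. Ordinary censoring at infection conditions on an event the drug is meant to change. Both points are right and shape the fix.

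**Conclusion.** The concern holds in conditional form. Section 6.1 implies that symptomatic COVID-19 and COVID-19 admissions enter the safety counts, and section 4 has no rule that separates them. If they are counted and the drug works as planned, the SAE hazard ratio reads about 0.62-0.94 with no true harm and about 0.87-1.82 under a true doubling. For total AEs, a true 1.2 reads about 0.96-0.97 at 15% background with 8% v 4% symptomatic infection, and less is lost when AEs are common. These sizes rest on the plan's 10% v 5% and on assumed hospitalised shares and background risks.

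A reader might go further and conclude that the safety analysis will hide harm. The documents do not show that: it requires inclusion, real efficacy, and non-COVID SAEs that are rare relative to COVID-19 admissions. The change should be made because it is cheap and settles a question that section 4 leaves open.

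**What to change.** 1. **Section 4.** Pre-specify AE and SAE comparisons that exclude events of RT-PCR- or IgG-confirmed SARS-CoV-2 infection, and report them beside the all-event comparisons.
2. **Identification rule.** Define these events by dates already collected (symptom onset, positive test, hospitalisation), not by investigator attribution after masking is released. Say how an infection without symptoms is dated, and that confirmation after day 60 (for example IgG at day 75) still counts for symptoms that began earlier.
3. **Estimator.** Treat confirmed infection as a competing event, with cumulative incidence by the Aalen-Johansen method rather than Kaplan-Meier with infection as ordinary censoring. State whether the accompanying hazard ratio is cause-specific or subdistribution.
4. **Definitions.** Reconcile the AE window and SAE criterion in section 6.1 with Appendix 3, and make sure the exceptions announced in section 6.2 are listed, including whether COVID-19 is one of them.

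**Cost.** One extra table and a short derivation rule; no new data field is needed. The downside is that drug-related events arising after infection appear only in the all-event version, so both versions are needed.

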3.1. Study design

Randomized triple-blinded multicentric clinical trial, conducted in parallel, with two arms:

The trial will be performed with health care workers (Physicians, Nurses, Respiratory therapists, or nurse assistants) free of SARS-CoV-2 infection prior, recent or at the time of the inclusion and who directly care for confirmed or suspected cases of COVID-19 in the emergency room, general COVID wards or intensive care units. A screening at baseline will be carried out in order to evaluate for eligibility by performing: SARS-CoV-2 RT-PCR, SARS-CoV-2 IgG antibodies, as well as, hemogram, creatinine, serum phosphorus, AST, ALT, ELISA for HIV, surface Hepatitis B antigen antibodies, qualitative pregnancy test (b-HCG). Once

eligibility is verified participants will be randomly assigned to either an intervention or a control group.

The interventions consists in the administration of Tenofovir/ Emtricitabine (300 mg / 200 mg daily during 60 days) + Personal Protective Equipment (PPE) and the control consists in the administration of placebo (1 tablet daily during 60 days) + Personal Protective Equipment (PPE)

All participants will have PPE recommended for the preventions of COVID-19 by the WHO which include mayo dress, nonfluid long sleeve gown, ocular protection with goggles, face shield or visor and surgical mask in procedures that do not aerosolize. N-95 respirators are required for procedure that generate aerosols. For detailed description see Table 2.

The re-use of N-95 respirators will be allowed according to CDC and WHO guidelines. This taking into consideration the shortage of supplies for the actual situation. The N-95 continuous use will be for 8 hours and the N-95 intermittent use will be allowed up to 5 times with the precaution of storage in a paper and plastic bag label them with the participant name and placed them in a plastic recipient at the end of shifts(48).

After baseline evaluation and confirming eligibility an initial visit and 4 follow up visits at day 20, 40, 60, 75 days will be carried out. See Table 1 and Graph 1.

In the case of presenting COVID-19 related symptoms at any time after enrolling a SARS-CoV2 RT-PCR will be performed between day 1 to 5 of the onset of symptoms and will be repeated it after 72 hours in case that the first one is negative. In the case of having any positive SARS-CoV2 RT-PCR or SARS-CoV2 IgG SARS-CoV2 infection will be confirmed and the intervention will be suspended.

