3.6.9. Procedure in case of presenting the primary outcome

If the volunteer, after the start of the study, has a positive result of RT-PCR or IgG for SARS CoV2, which confirms the infection by COVID 19, they will be contacted virtually or in person. During this intervention, the following actions will be carried out:

- You will be given information about your result, and you will be instructed to contact your occupational risk and health insurer.
- The presence of alarm signs (drowsiness, dyspnea, cyanosis) will be evaluated. In case of any of these symptoms are present, the patient will be instructed to attend the emergency service, to receive treatment in accordance with current national and institutional guidelines.
- The volunteer will be instructed to suspend the intervention product, and the masking will be released.
- National Public Health Surveillance System mandatory notification form will be filled out, the institution where the volunteer works will be informed, and the completed form will be sent.

- The volunteer will be informed that telephone follow-up will be carried out every 5 days until the symptoms are resolved or a maximum of six weeks after the diagnosis of COVID 19. In case of presenting any alarm sign during the follow-up, the patient will be recommended to attend the emergency department.

During the telephone follow-up, the volunteer's primary outcome (COVID 19 infection) will be classified as follows: asymptomatic, mild, moderate, or severe COVID. If the patient does not answer due to physical impossibility (e.g. intubation), communication with a companion or family member previously authorized by the patient will be sought.

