3.6.9 Study withdrawal criteria

The following criteria should determine the immediate withdrawal of the volunteer from the study:

- Grade 2 or greater kidney abnormalities at any time of follow-up.
- Clinical indication to start a drug with significant interactions with TDF/FTC during the development of the study.
- Presentation of any serious adverse event related to the intervention, defined by the physicians assigned to the study.
- Any Adverse Event (AE) that determines that the volunteer wishes to interrupt the intervention.
- That the volunteer voluntarily and for any reason decide to withdraw from the study.

If any of the previously mentioned criteria are met, the doctor assigned to the study in charge of the follow-up will immediately inform the coordinator of their respective center. The report of all AE will be made by the principal investigator of each center, in accordance with the INVIMA regulations and taking into account the Standardized Operating Procedures (SOP) established by the study.

In the event that the patient withdraws their consent, no additional monitoring will be possible. This situation will be reported immediately to the clinical monitor and monthly to the Institutional Research and Ethics Committee (CIEI).

3.6.10. Follow-up of volunteers with a positive pregnancy test at the end of follow-up

Despite the fact that TDF/FTC is a classification B drug in pregnancy, and its use is recommended as one of the antiretrovirals of choice in pregnant women with HIV (76), within this study it was defined to exclude pregnant women, or with the desire to become pregnant, to avoid exposure to this drug given its high placental transfer to the fetus.

There is no evidence in humans of teratogenicity with TDF/FTC, however there is evidence in monkeys, at doses twice as high as the therapeutic doses in humans, of decreased fetal growth and reduced fetal bone porosity within two months of initiation of maternal therapy; Regarding human studies, there is no demonstrated relationship with low birth weight, but there are conflicting results on the outcome of growth in childhood (77).

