In a randomized, double-blind, placebo-controlled trial of PrEP in African women, Mugo NR, and colleagues (78) evaluated the effect of TDF/FTC on pregnancy for HIV-uninfected women. Differences in the incidence of pregnancy, delivery outcomes, and infant growth were not statistically different for women who received PrEP with TDF alone, or combination of FTC + TDF compared to placebo at conception. Considering that PrEP was discontinued when pregnancy was detected and that the confidence intervals for delivery outcomes were wide, the authors did not commit to making definitive statements about the safety of PrEP in the period of periconception (78).

For the above reasons, if any volunteer presents a pregnancy at the end of the intervention period, a specific Informed Consent Form will be filled out to carry out a follow-up during the pregnancy.

4. Statistical analysis plan

Initially, a descriptive analysis of the information will be made, and measures of central tendency and dispersion will be reported according to the type of variables. In this phase, the similarity between the groups of the experiment will be evaluated and it will be calculated if there are differences in the groups due to chance.

Primary outcome

Taking into account that this study is a pragmatic clinical experiment, which will evaluate effectiveness, an intention-to-treat analysis will be carried out, to solve the main objective, the proportion of incidence of SARS-CoV-2 infection in each group will be determined at the day 75 post-randomization, estimated as the cumulative incidence of infection using the Kaplan Meier method.

Exposure of interest: Prophylaxis with TDF/FTC plus EPP vs placebo plus EPP.

Primary outcome: SARS CoV2 infection

Zero follow-up time (registration time in the registry): the time that the volunteer is randomized to the study interventions.

Follow-up time: All individuals have a follow-up until they present the primary outcome, or meet any of the withdrawal criteria, or up to 75 days after the zero follow-up time, if they do not present the outcome.

Event: SARS-CoV-2 infection.

Censorship: censorship occurs when the outcome is not presented, the two types of censorship will be: administrative censorship 75 days after randomization, or censorship for compliance with any of the criteria for withdrawal from the study, or loss of follow-up.

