Withdrawal of investigational product	Qualitative/nominal	Decision by investigator or patient to withdraw investigational product before planned.	0-Not applicable 1- Withdrawal due to kidney dysfunction. 2- Withdrawal due to need for new interacting medications. 3- Withdrawal due to development of any SAE deemed to be related to intervention. 4- Withdrawal due to any AE that makes the volunteer decide to interrupt investigational product. 5-Voluntary withdrawal.
Date of investigational product withdrawal	Quantitative/continuous	Date of discontinuation of investigational product, only if previous answer was other than 0	Day/month/year
Time to discontinuation of investigational product	Quantitative/discrete	Time between initiation of investigation product to discontinuation	Number of days
Severity of COVID-19	Qualitative/nominal	Classification of severity as follows: - Asymptomatic infection - Mild disease: defined as not requiring hospitalization. - Moderate disease: defined as requiring hospitalization outside of the ICU. - Severe disease: defined as requiring hospitalization in ICU.	1-Asymptomatic 2-Mild 3-Moderate 4-Severe
Date of hospitalization start	Quantitative/continuous	Date of hospitalization start	Day/month/year
Date of hospital discharge	Quantitative/continuous	Date of hospital discharge	Day/month/year
Date of ICU admission	Quantitative/continuous	Date of ICU admission	Day/month/year
Fecha de egreso del UCI	Quantitative/continuous	Date of ICU discharge or date of death	Day/month/year
Date of recovery from COVID-19	Quantitative/continuous	Recovery from COVID-19 defined as a minimum of 10 days after symptom start plus at least 72 hours of symptom improvement. If the patient died, record 00/00/00	Day/month/year
Final status	Quantitative/continuous	Record of volunteer status at the end of follow-up	0- Death 1- Alive
Date of end of follow-up	Quantitative/continuous	Date of end of follow-up	Day/month/year

References

1. Daihai H, Daozhou G, Zhuang Z, Peihua C, Yijun L, Lin Y. The attack rate of the COVID-19 in a year. :3–5.

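### As the SAP is worded, the any-reason discontinuation hazard ratio includes stops mandated by infections confirmed during dosing, while the Appendix 3 withdrawal variable has no code for them

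*Combined protocol and SAP*

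**What the plan says.** Section 3.3 lists the secondary outcome as "Discontinuation of using the intervention (TDF/FTC or placebo) for any reason". Section 4, under secondary outcomes, sets out the analysis: "The proportion of incidence of discontinuation of the intervention in each group, for any reason, will be determined at day 60 after randomization", by Kaplan-Meier, with a univariate Cox hazard ratio between arms. No exclusion or competing-event rule is attached.

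Two sections require the product to be stopped at infection. Section 3.1 says that on any positive RT-PCR or IgG "infection will be confirmed and the intervention will be suspended". Section 3.6.9 (procedure at the primary outcome) says "The volunteer will be instructed to suspend the intervention product, and the masking will be released".

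Appendix 3 defines the withdrawal variable as "Decision by investigator or patient to withdraw investigational product before planned". Its codes are 0 (not applicable), kidney dysfunction, interacting medication, related serious adverse event, adverse event leading the volunteer to stop, and voluntary withdrawal. Infection is not among them. The stop date is kept under this rule: "Date of discontinuation of investigational product, only if previous answer was other than 0". The separate list of interruption causes in Appendix 3 also omits infection.

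Section 4 does contain a rule that ends follow-up at infection ("All individuals have a follow-up until they present the primary outcome, or meet any of the withdrawal criteria"), but it is written under the primary outcome and is not repeated for discontinuation.

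**The concern.** The trial is planned on TDF/FTC halving infection. If infection-mandated stops count, placebo is expected to have about twice as many of them, so efficacy alone pulls the discontinuation hazard ratio below 1. Someone reading that ratio as evidence on how acceptable the drug is would be misled. An excess of stops for other reasons, including those under the withdrawal criterion "Grade 2 or greater kidney abnormalities at any time of follow-up", could be partly or wholly offset.

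The data definition adds a second difficulty. Site staff facing a mandated stop can enter 0, which leaves no date and no event, or use a code that does not fit, such as voluntary withdrawal. With code 0, nothing says the person is censored, so someone already off drug could remain in the risk set for stopping. Section 3.6.9 releases the masking at the same moment, so the choice of code could be made with the arm known.

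**Working it through.** **Planning inputs.** The documents give no expected figure for discontinuation. The only related stated figure is the sample size in section 3.4, which fixes the infection risks used here. For 0.10 vs 0.05, two-sided alpha 0.05 (sidedness is not stated) and power 0.80, the pooled two-proportion formula gives 435 per group and the unpooled formula 432. The plan states 429, within 3%. Raising 858 for 10% losses gives 858/0.9 = 954; the plan states 950. The inputs are therefore taken as written: 10% vs 5%, 475 per arm.

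**Which infections force an early stop.** Section 3.6 places the universal RT-PCR on day 60, the last day of dosing, and IgG on days 40 and 75. Infections first found on day 60 or 75 force no early stop. Let f be the share of infections confirmed while still on drug. Section 1.3 reports 18% to 46.5% asymptomatic. If all symptomatic infections and no others stop the drug, f = 1 - 0.18 = 0.82 down to 1 - 0.465 = 0.535. A low case of f = 0.25 allows for symptomatic infections confirmed late or after dosing.

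**Assumption.** The risk of stopping for other reasons by day 60 is not in the documents. It is set at 5% on placebo; a range follows below.

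**Formula.** With constant hazards, h(p) = -ln(1 - p), and

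any-reason HR = [h(other, TDF/FTC) + h(0.05f)] / [h(other, placebo) + h(0.10f)].

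With h(0.05) = 0.0513 for other stops in both arms:

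| f | h(0.10f), placebo | h(0.05f), TDF/FTC | HR, equal other stops | Chance of significance favouring TDF/FTC |
|---|---|---|---|---|
| 0.82 | 0.0856 | 0.0419 | 0.0932/0.1369 = 0.68 | about 48% |
| 0.535 | 0.0550 | 0.0271 | 0.0784/0.1063 = 0.74 | about 28% |
| 0.25 | 0.0253 | 0.0126 | 0.0639/0.0766 = 0.83 | about 11% |

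The last column comes from log-rank simulation with 475 per arm for the first two rows and from the normal approximation for the third, where simulation gives 12%. Under no difference it should be 2.5%. Censoring at the infection-mandated stop brings it to 2-3%.

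**How much excess can be hidden.** The any-reason HR equals 1 when the true HR for other stops is r = 1 + [h(0.10f) - h(0.05f)]/0.0513:

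- f = 0.82: r = 1 + 0.0437/0.0513 = 1.85, i.e. 9.1% vs 5%
- f = 0.535: r = 1 + 0.0279/0.0513 = 1.54, i.e. 7.6% vs 5%
- f = 0.25: r = 1 + 0.0127/0.0513 = 1.25, i.e. 6.2% vs 5%

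**If other stops truly double, 5% to 10%.** Here h(0.10) = 0.1054 and the true HR is 0.1054/0.0513 = 2.05. The any-reason HR is 0.1472/0.1369 = 1.08, 0.1325/0.1063 = 1.25 and 0.1179/0.0766 = 1.54 for the three values of f. Its power is about 6%, 21% and 52%. Censoring at infection gives 83-85%.

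**Sensitivity to the assumed 5%.** With equal other stops and f from 0.82 to 0.535, the any-reason HR is 0.59-0.63 if the other-stop risk is 2% and 0.77-0.83 if it is 10%. For a doubling from 10% to 20% the HR is 1.39-1.56 with power 62-83%, so the masking is milder there.

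**If the Appendix 3 codes supply the events.** Infection stops coded 0 are not events, and this distortion does not arise.

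**The case against.** The strongest reply is that Appendix 3, which section 3.6.7 names as the source of operational definitions, leaves infection out. Its withdrawal codes mirror the study withdrawal criteria, where infection is also absent. If events come from that variable, forced stops never enter the hazard ratio. This stands as a limit: the documents conflict, and it cannot be said that the ratio will count these stops. It does not settle the matter, because section 4 says any reason and nothing says which definition governs or how a person stopped for infection leaves the risk set.

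Any-reason discontinuation is also a stated objective (section 2.2) and a legitimate descriptive outcome. The plan never calls it tolerability; safety has its own adverse-event hazard ratios, and creatinine is graded separately. This stands too, and is why the any-reason outcome should stay.

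A reader might infer two stronger things. One is that every infection forces a counted stop. The testing schedule contradicts this, since infections first found on day 60 or 75 come at or after the last dose. The other is that the ratio will favour TDF/FTC even when the drug is stopped more often for other reasons. That depends on the assumed other-stop rate and on f, neither of which the documents give. At 5% and f = 0.25 it fails once the true HR exceeds about 1.25. The safety review in section 5.1.1 reports no difference in adverse events from placebo (OR 1.01), so a doubling of other stops is a stress case, not an expectation.

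**Conclusion.** The point holds in a limited form. On the wording of section 4, the discontinuation hazard ratio mixes stops mandated by infections confirmed during dosing with all other stops. The Appendix 3 variable cannot record the former correctly. If they are counted and the drug performs as planned, equal other stops at an assumed 5% give an HR of about 0.68 to 0.83 and roughly a 48% to 11% chance of a significant result favouring TDF/FTC, for f from 0.82 to 0.25. A moderate excess of other stops could be hidden. These sizes rest on constant hazards, the planned 10% vs 5%, and an other-stop rate and f that the documents do not supply. Severity is minor: one secondary outcome is affected, and the primary analysis and sample size are not.

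**What to change.** - Keep the any-reason proportion as the listed outcome, reported by arm and split by reason.
- In section 4, add a between-arm Cox comparison of stops before day 60 for reasons other than confirmed SARS-CoV-2 infection, censoring at the infection-mandated stop (a cause-specific hazard ratio). Report cumulative incidence alongside it, treating the infection-mandated stop as a competing event.
- In Appendix 3, add an infection code to the withdrawal variable and record a stop date with it.

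The cost is a paragraph of SAP text, one CRF code and one extra secondary analysis. Records already collected can be classified from the dates of positive RT-PCR and IgG. The downside is that the added comparison covers a narrower event than the listed outcome, so the two must be reported side by side.
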